12.3.2.2 Interim Analysis

Interim analysis: No formal interim analysis plan is necessary for this feasibility trial of limited duration for subject participation (3 months) and minimal risk to participants (telephone calls to engage participants in continuing care plans).

12.3.3 Collection and Reporting of Serious Adverse Events

12.3.3.1 Adverse Events - Definitions

An *adverse event* (AE) is any reaction, side effect, or untoward event that occurs during the study, whether or not it is considered study-related or clinically significant. AEs will include events reported by the patient or observed by clinic or study staff. A new illness, symptom, sign, or worsening of a preexisting condition or abnormality is considered an AE. Stable chronic conditions that were present prior to study entry and do not worsen are not considered AEs.

A serious adverse event (SAE) is an adverse event (as defined above) that results in one of the following outcomes: Death, life-threatening, persistent or significant disability/incapacity, requires or prolongs hospitalization and a congenital anomaly/birth defect. Important medical events that may not result in death, be life-threatening, or require hospitalization may be considered serious adverse events when, based upon appropriate medical judgment, they may jeopardize the patient and may require medical or surgical intervention to prevent one of the outcomes listed in this definition.

Requires or prolongs hospitalizations does not include hospitalizations related to normal child birth, elective hospital admissions scheduled prior to the study and hospitalization for an elective procedure or Emergency Room visits.

A related adverse event is an AE that is a result of the patient's participation in this study and/or a result of study intervention.

12.3.3.2 Collection and Recording of Serious Adverse Events

AEs meeting serious criteria (as defined in 12.3.3.1) will be collected from the time

of randomization through the 13-week follow-up visit and captured on the CRF (refer to section 11.10). The SAE CRF will include a description of the event, the date of onset, the severity of the event, whether or not the event is study related, and the outcome of the event. All CTPs should have a consulting physician available to review AEs in order to determine their seriousness and causality. Non-physician LIs/PIs are expected to obtain medical consultation as necessary.

All SAEs that are both serious and study related (result from the patient's participation and/or related to study intervention) will be reported by fax to NIDA/CCTN Medical Monitor, the lead investigator, [name], and DCRI Safety Surveillance in accordance with section 12.3.3.3. All SAEs will be followed by study investigators until event resolution, stabilization, or through the completion of the final 13-week follow-up visit, whichever occurs first.

Any AE that does not meet SAE criteria as defined in the protocol will not be captured for the purposes of this research study.

12.3.3.3 Expedited Reporting of SAEs

SAEs that are related to study intervention or/and participation must be reported within **24 hours** of the learning of the event according to the following procedures:

Initial notification of the event should be reported by fax to the following:

NIDA/CCTN Medical Monitor [contact] [contact]

[name], MBA, Lead Investigator

[contact] [name]

[contact]

DCRI Safety Surveillance [contact] [contact]

The fax notification should include a Serious Adverse Event Report Form and a copy of the SAE CRF page along with copies of any applicable supporting documentation, if available. DCRI Safety Surveillance will review and data base the information received, query the submitting node for missing and/or additional information, write a case summary and obtain Medical Monitor review. The DCRI Safety Surveillance Medical Monitor will perform a medical review of the SAE data, perform an independent evaluation of causality and seriousness, query DCRI Safety Surveillance for any additional information needed from the node, and approve the case summary within 2 business days of initial receipt of the

SAE form. DCRI Safety Surveillance will provide a copy of the SAE Report Form, SAE CRF page, case summary, any applicable supporting documentation to the lead investigator and the NIDA Medical Monitor within 5 calendar days of initial receipt of the SAE forms.

The initial SAE report should include the relationship (causality) to study intervention and/or to the patient's involvement in the study. This assessment should be determined by the principal investigator. In the case where the principal investigator is not a physician, this assessment must be made by the delegated qualified physician for the CTP. All SAE forms must also include the principal investigator's signature, or in the case where the principal investigator is not a physician, the signature of the delegated qualified physician for the CTP making the assessment of causality. If the principle investigator or qualified physician is not available to sign the form within 24 hours of the site's knowledge of the event, please fax the SAE Report Form and SAE CRF within 24 hours and send a signed form as soon as it becomes available.

DCRI Safety Surveillance will continue to work with the site to obtain all relevant information for the SAE and/or until the final outcome is determined. A follow-up Serious Adverse Event Report Form and SAE CRF page should be sent as soon as any additional significant information concerning the SAE in the same format and timeframe (within 24 hours) as outlined above. Events not resolved at the end of the trial will have an outcome of "ongoing".

Note: Reports and supporting documentation will be sent by the site in a blinded fashion, and the participant will only be identified by the participant number on each page of supporting information.

The investigators in this study are responsible for promptly reporting all events meeting the defined SAE criteria above, so that NIDA can comply with regulations and adequately monitor the safety of participants. Local IRB procedures and requirements for the reporting of AEs and SAEs may differ. It is important that the staff at each participating node be aware of the requirements of their IRB and report AEs and SAEs as required.

The DSMB will review all relevant safety data as directed by the NIDA/CCTN Medical Monitor and make recommendations of actions required and/or changes needed to the protocol, as necessary. These recommendations will be communicated to all nodes by the lead investigator, as needed.

12.3.4 Data Management QA Plan

A detailed document that contains the Data Management QA Plan will be maintained at the Duke Clinical Research Institute, the Lead Node's Data Management Center. This document will describe the procedures, i.e., data entry, storage and manipulation of the

data, and the output of data, which are used to ensure that the information collected, is the same as the information sent to NIDA.

12.4 Study Documentation and Records Retention

Study documentation includes all case report forms, data correction forms, electronic data files, workbooks, source documents, monitoring logs and appointment schedules, sponsor-investigator correspondence and regulatory documents (e.g., signed protocol and amendments; Ethics Review Committee or IRB correspondence, approved consent form and signed participant consent forms; and clinical supplies records).

Whenever possible, the original recording of an observation should be retained as the source document. However, a photocopy is acceptable provided that it is a clear, legible and an exact duplication of the original document.

Government agency regulations and directives require that the investigator must retain all study documentation pertaining to the conduct of a clinical trial for at least 6 years or until the study is completed, whichever is longer.

12.5 Confidentiality

To safeguard confidentiality, the Lead Node PI will apply for a Certificate of Confidentiality from NIDA on behalf of all participating sites.

12.5.1 Confidentiality of Data

By signing this protocol, the investigator affirms to the sponsor that information furnished to the investigator by the sponsor will be maintained in confidence, and such information will be divulged to the IRB, Ethics Review Committee or similar or expert committee, affiliated institution, and employees only under an appropriate understanding of confidentiality with such board or committee, affiliated institution, and employees.

12.5.2 Confidentiality of Study Records

By signing the protocol, the investigator agrees that within local regulatory restrictions and ethical considerations, NIDA (the study sponsor) and its representatives, or any regulatory agency may consult and/or copy study documents in order to verify case report form data.

12.5.3 Confidentiality of Counselor Phone Calls

During the pre-discharge meeting for TCG participants and as deemed appropriate during the TELE procedure, the counselors will clarify specific calling guidelines with each participant as a means to maintain the participants' confidentiality. The counselors should list all restrictions for the telephone calls noted by the participant. The counselor should address any concerns or questions participants might have regarding the call process

during the pre-discharge meeting or during the subsequent calls to avoid problems later. Participants should have reassurance that their confidentiality will be strictly maintained, that no information will be disclosed to anyone, with the exception of threats of self-harm or suicide, child/elder abuse, or domestic violence. The purpose of the call procedure is to encourage the participant to engage in continuing care activities, not to collect information to disclose to anyone. With the exceptions noted above, no information will be disclosed to anyone, including the primary care counselor or residential facility. Participants should be encouraged to disclose any pertinent information themselves, with support and encouragement from the TELE counselors. Reassurance may help reduce the participant's uncertainty or anxiety about being contacted.

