10.4 Intervention after Discharge

Following discharge, a total of 7 telephone contacts at weeks 1, 2, 4, 6, 8, 10, and 12 will be made by the TELE counselor to all participants randomly assigned to the TCG. Each contact will follow the scripted procedure outlined in the Counselors Manual. The same procedure will be followed upon each contact. Up to 3 attempts will be made to contact the participant for each of the 7 scheduled calls, regardless of the outcome of the previously scheduled call.

Unless consent to participate is expressly revoked by the individual, he or she will continue to be contacted as scheduled. Attempts to contact the participant and the outcome of the call will be recorded on the participant contact form in the CRF. The SCG participants will not be contacted by the TELE counselor following their pre-discharge session.

A portion of calls will be recorded and at least 10% of successful calls will be randomly selected and scored for fidelity to the intended call procedures. Each node supervisor will provide supervision to the TELE counselor, per standard practice for the particular program.

In order to provide standardization across all TCG calls, the TELE Counselors Manual provides directions for conducting these calls. Information obtained during the course of the call will not be used as research data with the exception of serious adverse events. These events disclosed by the participant will be documented and reported as described in section 12.0.

The manual also provides minimal instructions for handling medical emergencies such as suicidal threats. Each facility is expected to have a written plan in place for emergency situations. If a plan is not in place, a procedure will be developed by the facility and should be available for review by the node quality assurance (QA) monitor prior to enrollment. Each facility has the responsibility for training its research staff on the facility's emergency plan.

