11.10 Serious Adverse Events CRF

Serious adverse events, as defined in section 12.3.3.1, if reported to the TELE counselor during telephone contacts made at weeks 1, 2, 4, 6, 8, 10, and 12, or as elicited by the research assistant during the 13-week follow-up visit, will be addressed by the TELE counselor or the research assistant. Serious adverse events (which occurred from the time of randomization through the 13-week follow-up visit, and not previously recorded) which are reported to the TELE counselor during the scheduled telephone calls, or which are elicited by the research assistant during the 13-week visit, will be recorded on the SAE CRF and reported, as described in section 12.3.3.2.

Prior to study implementation, each site will have a documented plan describing their procedures in cases of suicidal or homicidal threats or attempts or other medical emergencies. During the course of the intervention period and at the follow-up visit, if participants are found to be in acute need of psychiatric attention for threats of these types or to have any condition requiring medical attention, the participant will be referred per the CTPs documented plan to community referral resources, including a medical care facility, readily available community hotlines, or other appropriate resources.

All SAEs determined to be related (refer to section 12.3.3.3) are to be brought to the attention of NIDA/CCTN medical monitor, the Lead Node medical monitor, and the local node/site PI within 24 hours of learning of the event and the local Institutional Review Board (IRB) per local requirements.

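### The confidentiality assurance for telephone calls in section 12.5.3 omits serious adverse events, which sections 10.4, 11.10 and 12.3.3 require to be recorded and reported

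*Protocol*

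**What the plan says.** Section 12.5.3 of the Protocol covers the confidentiality of counselor calls. Participants are to be reassured that "no information will be disclosed to anyone, with the exception of threats of self-harm or suicide, child/elder abuse, or domestic violence". The section describes the purpose of the calls as encouragement, "not to collect information to disclose to anyone", and then repeats the ban: "With the exceptions noted above, no information will be disclosed to anyone", with the primary care counselor and the residential facility named among those barred. It does not mention SAEs and does not refer to any of the safety sections.

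Section 10.4, on the intervention after discharge, takes a different line: "Information obtained during the course of the call will not be used as research data with the exception of serious adverse events". It continues: "These events disclosed by the participant will be documented and reported as described in section 12.0".

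Section 11.10 covers SAEs "which are reported to the TELE counselor during the scheduled telephone calls", together with those elicited at the week-13 visit, and says that they "will be recorded on the SAE CRF and reported, as described in section 12.3.3.2".

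Sections 12.3.3.2 and 12.3.3.3 then name the recipients. SAEs judged study related are faxed within 24 hours of the site learning of them to the NIDA/CCTN medical monitor, the lead investigator and DCRI Safety Surveillance.

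**The concern.** The counselor works under two sets of instructions that disagree for one class of information. If a participant mentions a hospital admission on a call, sections 10.4 and 11.10 require it to be recorded and 12.3.3 may require it to be reported. Section 12.5.3 has the counselor promise that such information goes to nobody.

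Two things are at stake. The first is honesty toward participants: people leaving substance abuse treatment are given an assurance that the protocol itself requires staff to depart from. The second is the completeness and timeliness of safety data. SAEs are the only adverse events this trial collects, and the DSMB's safety review under 12.3.2.1 rests on SAE listings. A counselor who took the confidentiality paragraph at its word could hold an event back.

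**Working it through.** The point rests on no sample-size, power or error-rate figure, so the check is to set the sections side by side.

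1. **Is the list in 12.5.3 closed?** Yes. It names the exceptions and then bars everything else by pointing back to them ("With the exceptions noted above, no information will be disclosed to anyone, including the primary care counselor or residential facility"). There is no general clause for study procedures or safety reporting.

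2. **Do the exceptions cover SAEs?** Only in part. A suicide attempt might fall under the self-harm exception. The SAE definition in 12.3.3.1 is much wider, taking in death, life-threatening events, lasting disability, hospitalization, congenital anomaly and other important medical events. An ordinary medical admission is an SAE and matches none of the exceptions.

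3. **Does recording and reporting count as disclosure to someone?** Yes.
   - Every recorded SAE goes on a CRF, and section 14.1 sends CRFs to the Lead Node Data Management Center.
   - Section 12.3.3.2 expects a consulting physician for the treatment program to be available to review events for seriousness and causality.
   - Study-related SAEs also go to the three recipients named in 12.3.3.
   - Section 12.3.2.1 provides SAE listings to the DSMB.

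4. **Can both rules be kept for the same event?** Take an ordinary hospitalization first mentioned on a scheduled call. Under 10.4 and 11.10 it must be recorded and handled under 12.3.3.2. Under 12.5.3 it may be told to nobody. As written, one rule has to give way.

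5. **What happens if the counselor holds the event back?** The next planned point for eliciting SAEs is the week-13 visit. Table 1 puts the first call at days 4–10 after discharge, the seventh at days 81–87, and the visit at days 88–116. The gap between a call and a completed visit can therefore run from 88 − 87 = 1 day to 116 − 4 = 112 days. For a study-related SAE, most of that range lies beyond the 24-hour limit. If the visit is missed, section 10.6.3 plans verification of continuing care and possibly of criminal justice activity. It plans no SAE inquiry.

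**The case against.** The strongest reply is that the protocol's intent is not in doubt. Section 10.4, which governs how calls are made, states the SAE exception outright, and 11.10 and 12.3.3 repeat the duty in mandatory terms. A sensible reader would let several specific safety rules prevail over one general confidentiality paragraph. This stands, and it is why under-reporting is a secondary risk and not the expected result. It does not rescue the assurance: the more faithfully counselors follow 10.4, the more plainly the promise in 12.5.3 is wrong.

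A second reply is that 12.5.3 is aimed at treatment staff and outsiders, since the recipients it names are the primary care counselor and the residential facility. But the sentence bars disclosure to anyone and gives those two as included examples. Section 12.3.3.3 does limit SAE reports to the participant number, which reduces identifiability, but the promise is that no information is passed on, not that it is passed on without a name.

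Third, the Counselors Manual and the consent form are not part of the text at hand, and either may already mention SAE reporting. That is fair. What participants are actually told cannot be confirmed, and the point is confined to what 12.5.3 says they should be told.

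A reader might also infer a larger effect:

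- **Scale.** The planned 180 participants × 7 calls = 1,260 scheduled calls, and 20% of 180 = 36 possible missed visits. These count calls and people, not SAEs. The 20% in section 13.3.1 is a ceiling for all randomized participants, and applying it to one arm assumes equal loss between arms.
- **Events lost altogether for those who miss week 13.** This is not supported. Table 3 has the SAE CRF collected at termination of study participation, section 10.6.1 describes a scheduling call by the research assistant, and section 10.5 keeps a log of contacts that participants initiate. These are weaker than a completed visit, but they are not nothing.
- **Sites reporting SAEs at different rates.** Nothing in the protocol shows this. Section 15.1 has the Lead Node train the counselors from one manual, which makes divergence less likely.

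**Conclusion.** The contradiction is real. Section 12.5.3 directs an assurance that sections 10.4, 11.10 and 12.3.3 require staff to break whenever an SAE outside the listed exceptions is disclosed on a call. The main consequence is an assurance that is untrue as worded. The secondary consequence is a possible delay or omission if a counselor reads 12.5.3 literally, most relevant for participants who go on to miss the week-13 visit.

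The number of SAEs affected cannot be stated, because the protocol gives no SAE rate. The 24-hour deadline concerns only study-related SAEs, in a trial that section 12.3.2.2 describes as minimal risk. No endpoint, efficacy analysis or sample-size figure changes. The conclusion assumes that 12.5.3 means what it says about disclosure to anyone, and that the manual and consent form do not replace it.

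**What to change.** Reconcile section 12.5.3 with 10.4, 11.10 and 12.3.3. Add to the exceptions that serious adverse events are recorded and reported as described in section 12.3.3, and include the same statement in the assurance given at the pre-discharge meeting. Then check that the Counselors Manual and the consent wording say the same. This adopts a duty the protocol already imposes and creates no new one.

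The cost is one sentence in the protocol, with matching edits to the manual and consent form if they repeat the narrower promise. Participants told of this exception may be slightly less open on calls.

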13.0 ANALYTICAL PLAN

13.1 Analytical Considerations

This clinical investigation serves 2 purposes: (1) to evaluate the feasibility of the study within the CTN and (2) to explore the effectiveness of TCG as compared with the SCG. The later analysis will be used to augment the feasibility data by providing preliminary findings that can be incorporated in the power and sample size determinations for a future large-scale study. Descriptive statistics will be used to address the primary feasibility issues, while a combination of descriptive statistics and hypothesis-testing methods will used to explore treatment effectiveness.

Descriptive statistics presented for continuous variables will include the mean \pm 1 standard deviation, the median and 25th and 75th percentiles, as well as 95% confidence intervals of the mean. Categorical variables will be presented as proportions, with 95% confidence limits. Inclusion of the confidence intervals will allow investigators to ascertain the values of the point estimates likely to be found in a larger efficacy trial. Summary data will be presented across all sites, as well as by site.

13.2 Feasibility Indicators

Feasibility information will be gathered to determine the proportion of (1) total eligible participants who volunteer and thus consent to participate in the study, (2) consenting participants completing all required residential treatment and baseline assessments, (3) consenting participants meeting the eligibility criteria, (4) consenting participants randomized into one of the 2 treatment conditions, (5) randomized participants contacted by phone after discharge, (6) randomized participants who could be contacted for follow-up visit, and (7) randomized participants completing the follow-up during the visit.

In order to determine 1–7 above, we will need to collect the following information:

- Number of participants entering the residential program
- Number asked to participate in the protocol
- Number agreeing to participate in the protocol
- Of those who agree, the number who complete the baseline assessments
- Of those who agree, the number who complete the residential program

- Of those who complete the residential program, the number who meet eligibility criteria for the study
- Number of participants randomly assigned to a treatment group;
- Number of patients successfully contacted to schedule week 13 visit
- Number of week 13 visits completed for the randomized patients
- Of those who complete a week 13 visit, time interval between discharge and the follow-up visit

For the TCG participants, logs of phone calls and attempted contacts will be compiled to examine the proportion of participants in which the 7 phone contacts were delivered and the average number of phone contacts delivered per participant. To determine whether it is possible to reach participants by telephone after they have been discharged from residential substance abuse care, the following data will be collected:

- Number of scheduled phone contacts attempted
- Number of scheduled phone contacts completed (delivered)

For the TCG condition, fidelity procedures have been included in the study to evaluate whether counselors who deliver the calls can conduct these calls in a standardized manner when provided with a structured "script." A portion of calls will be recorded and at least 10% of successful calls will be randomly selected by the Lead Node statistician for analyses for treatment integrity and fidelity.

If the above items are successful in terms of their implications for feasibility, what is the magnitude of the "effect size" of such a study design? This will be done by assessing the efficacy outcomes from this preliminary study (which reflect actual participant outcomes) and comparing results from various other analyses to arrive at a reasonable estimate of the effect size.

Taken together, the results derived from the feasibility indicators will be reviewed by experienced investigators at the nodes and in the leadership of the CTN, and decisions will be made concerning whether the pattern of participant availability is amenable to the conduct of a full-scale study of the telephone protocol.

